6.1 Study Intervention

(1) Implement routine care in the control group

Children in the control group and their parents received routine care and health education guidance, as well as guidelines and suggestions on physical activity of patients with malignant tumors provided by the investigator, and issued health knowledge education manuals. In addition, the investigator and other members of the intervention team did not provide information on parent-child activities;

(Ii) The experimental group received the family-based parent-child physical activity intervention combining online and offline, specifically as follows:

(1) Information support:

I . Establish and use wechat groups

After obtaining the informed consent, the children with cancer and their parents were invited to join the wechat group, and the popular science of physical activity related knowledge was regularly pushed to the children and their parents every week. Children and their parents have any questions can be asked to the intervention team members in the group. In addition, every Monday, the researchers sent the physical activity clock in the group, inviting the children and parents to record after completing the physical activity.

II . Create and use a wechat official account

Create a wechat official account, and push tweets and video content related to physical

activity every Thursday, Saturday and Sunday morning.

III . Offline group parent-child activities

Inform the children with cancer and their parents to follow up every 4 weeks, and organize the follow-up children and their parents to participate in offline group parent-child activities.

(2) Personnel support:

I . Promote parental participation

- ① Improve parents 'physical activity knowledge, belief and ability: through wechat group, wechat public account and other ways, increase parents' understanding of children's physical activity knowledge, improve their belief and ability to supervise and participate in children's physical activity.
- ② Increase parent-child activities to promote parents' participation: push a variety of parent-child physical activities, such as two-person aerobics, two-person ball sports, and outdoor sports requiring family participation (such as mountain climbing), etc.
- ③ Organize family competitive games to promote parent-child interest.
- ④ Enhance parent-child communication, and jointly develop solutions to various problems.

II . Strengthen the role between families —— peer influence

- ① WeChat group communication, enhance the information interaction and emotional support between peers.
- ② Family competition, improve the role of role model.

III . Strengthen the role of medical staff —— Medical staff support

- ① Information and technical support: medical staff shall provide relevant information, venues and goods to the child and their parents.
- ② Emotional support: When children and parents have problems or emotional needs, intervention team members should provide timely answers and encouragement online; at monthly follow-up, researchers will provide separate face-to-face interviews to help them solve their problems.
- ③ Other support: In the offline activities, the medical staff also actively participate in the demonstration for the children and their parents.

(3) The intervention program lasts for 12 weeks and is follow-up for 3 months after the completion of the intervention.

6.2 Study Intervention Adherence

Compliance assessment method: Monday morning 08:00 researchers in WeChat group send physical activity clock table, invite children and parents after complete physical activity after the corresponding record, to calculate the amount of exercise per week, if reach 3 times a week, 30 minutes of parent-child activity, is to complete the activity plan this week.

7. Measurements

This study mainly adopts the form of paper questionnaire data collection, the tools to be used including the children's socio-demographic data and disease related data, parents general information, children's leisure activity questionnaire, international

physical activity questionnaire, physical activity self-efficacy scale, physical activity enjoyment scale and physical activity social support scale.

- (1) Collect the questionnaire, researchers use unified guidelines and instructions to encourage malignant children and their parents to fill in the questionnaire and scale; For the participants who could not fill in the questionnaire by themselves, the participants will answer the contents of the questionnaire items, and the data collectors will fill in the questionnaire for them;
- (2) After recruiting eligible children and their parents according to discharge standards and obtaining informed consent, Collect the baseline (T0) data, Including children's general data, physiopathological indicators, physical activity questionnaire, physical activity self-efficacy scale, physical activity enjoyment scale, family support questionnaire and general data of children's parents, physical activity questionnaire; Physical activity questionnaires, physical activity self-efficacy scale, physical activity enjoyment scale and physical activity questionnaires of parents were collected at the end of intervention week 4 (T1) and week 8 (T2); At the end of the intervention (T3), the physical activity indicators, physical activity questionnaire, physical activity self-efficacy scale, physical activity enjoyment scale, family support questionnaire and physical activity questionnaire of the parents were collected; Three months after the intervention (T4), Phyopathological indicators, physical activity questionnaires, family support questionnaires and physical activity questionnaires of parents were collected.

References

- [1] C-G Lam, Howard S-C, Bouffet E, et al. Science and health for all children with cancer[J]. *Science*, 2019, 363(6432): 1182-1186.

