The Effects of Parent-Child Activity Program on Physical Activity of Children With Cancer

March 31, 2024

1. Summary

Study Population: Children diagnosed with malignant tumors aged 6 to 14 years.

Outcome measures: ① Main outcome measures: physical activity behavior in children with cancer; ② secondary outcome indicators: height, weight, BMI, body fat, muscle, self-efficacy of physical activity, physical activity enjoyment, perceived social support in physical activity, and physical activity of parents.

Study Intervention: ① Control group: the children and their parents receive routine care and health education guidance, receive physical activity guidelines and suggestions for patients with malignant tumors provided by the researchers, and issue health knowledge education manual. In addition, the researchers and other members of the intervention team do not provide information about parent-child activities; ② Experimental group: the experimental group receives online and offline family-based parent-child physical activity intervention. It includes participating in offline group parent-child activities during hospitalization, including family competitive games and knowledge contests, etc., popularizing science of physical activity and parent-child sports activities to children and parents regularly after discharge, and pushing tweets, sports and practice videos related to physical activities and parent-child sports activities. Exercise were followed every 4 weeks and assessed for the previous session. The intervention protocol lasts 12 weeks and is followed up 3 months after the intervention is completed.

Sample size: with physical activity as the outcome indicator, the sample content was used to estimate the sample content calculation method, and the test level α was set to

0.05, and the control degree was 90%. According to the results of the literature review, 20.8621 subjects in the experimental group and the control group, considering 20% lost to follow up, so at least 27 subjects in the experimental group and the control group.

2. Introduction

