Scholars have developed various intervention programs for the physical inactivity of patients with childhood malignancy, Showing multiple health benefits, However, the effects of various intervention programs are not the same: the intervention programs supervised by professionals in the hospital has strict requirements on time, site and personnel; Physical activity plans at home due to lack of knowledge, inadequate supervision, Lead to low intervention compliance and no significant effect; With the development of mobile health and electronic health devices in recent years, Such as SMS, apps, real-time video calls, virtual reality technology, It offers broad prospects for remote intervention of physical activity in childhood malignancies^[12,13]. But home physical activity programs for children still require parental participation, guidance and supervision. The latest research shows that the parents to participate in the activity plan to improve compliance and intervention effect has positive influence: in professionals (such as medical staff or sports coach), under the guidance of parent-child activity plan participation and completion rate is as high as 90%, after intervention children with physical function, cardiopulmonary function, fatigue, quality of life, etc^[14]. However, such studies are still in the exploratory stage, the number of related studies is small, and the long-term health effects of the intervention are unknown, requiring more data to support them.

Cross-sectional studies show that physical activity in children with cancer is associated with multiple factors, including physical and psychological factors, family

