5.2 Study design process

Establish an intervention team composed of researchers and qualified doctors and nurses, and evaluate the intervention members. Study subjects were recruited according to the exclusion criteria, and after obtaining informed consent and signing the consent form, the study subjects were included in the control group and experimental group. In order to prevent contamination, it was divided into control group and experimental group according to the chronological order, that is, the experimental group was included first, and in the experimental group, the control group was included after the sample size is sufficient. The control and experimental groups received usual care and parent-child activity intervention. Data were collected and analyzed at enrollment (T0), 1 month (T1), 2 months (T2), 3 months (T3), and 3 months (T4) after the intervention.

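### Section 7 leaves the self-efficacy and enjoyment scales out of the T4 visit, so maintenance of these two secondary outcomes at 3 months cannot be estimated

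*Combined protocol and SAP*

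**What the plan says.** The summary (section 1) declares both scales as outcomes: "secondary outcome indicators: height, weight, BMI, body fat, muscle, self-efficacy of physical activity, physical activity enjoyment". Section 5.1.1, hypothesis 2, expects the programme to raise both. Section 5.2 gives the visits without naming instruments: "Data were collected and analyzed at enrollment (T0), 1 month (T1), 2 months (T2), 3 months (T3), and 3 months (T4) after the intervention".

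Section 7 gives the content of each visit. At baseline the list is the fullest: "Including children's general data, physiopathological indicators, physical activity questionnaire, physical activity self-efficacy scale, physical activity enjoyment scale, family support questionnaire", together with the parents' data. T1 and T2 keep the child and parent activity questionnaires and the two scales. The end-of-intervention visit reads "At the end of the intervention (T3), the physical activity indicators, physical activity questionnaire, physical activity self-efficacy scale, physical activity enjoyment scale", then family support and parent activity. The T4 list is "Three months after the intervention (T4), Phyopathological indicators, physical activity questionnaires, family support questionnaires and physical activity questionnaires of parents were collected". Neither scale is in it, and no reason is given.

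Section 5.4.2 item ④ plans a mixed-design analysis of variance, or generalized estimating equations if its assumptions fail, for activity, self-efficacy, enjoyment and social support. It includes time and intervention-by-time effects. It does not say which visits enter for which outcome.

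**The concern.** T4 is the only visit after the programme stops, so it alone can show whether an effect outlasts the contact with the intervention team. Section 2.1 builds the programme on a model in which self-efficacy and enjoyment, along with parental influence, are the main levers on children's activity. If activity holds up or falls away at T4, the natural next question is whether these two levers did the same. Without the scales at that visit the trial cannot answer it.

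The omission does not look like a deliberately light visit. Body measures and family support, both skipped at T1 and T2, are collected at T4. Scale responses that were never collected cannot be recovered at the analysis stage, by either of the two methods in item ④.

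**Working it through.** No figure in the plan bears on this point, so the check is a tabulation of section 7 by instrument and visit. I take the family support questionnaire in the visit lists to be the social support scale named among the tools in section 7 and in 5.4.2.

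| Measure | T0 | T1 | T2 | T3 | T4 | Visits |
|---|---|---|---|---|---|---|
| Child activity (primary) | yes | yes | yes | yes | yes | 5 |
| Parent activity | yes | yes | yes | yes | yes | 5 |
| Self-efficacy | yes | yes | yes | yes | no | 4 |
| Enjoyment | yes | yes | yes | yes | no | 4 |
| Family support | yes | no | no | yes | yes | 3 |
| Body measures | yes | no | no | unclear | yes | 2 or 3 |

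**What can be estimated at T4.** Child activity, parent activity, family support and body measures can. Self-efficacy and enjoyment cannot.

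**What can be estimated at T3.** Child activity, parent activity, self-efficacy, enjoyment and family support can. Body measures depend on how one term is read (see below).

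**Number of children affected.** Planned enrolment is 2 × 27 = 54 (5.4.1). With the plan's 20% loss, about 0.8 × 54 = 43.2, or 43 children, would be expected to reach the end of follow-up. On either basis, the number with T4 scores on the two scales is 0.

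**Effect on the item ④ model.** With two groups and k visits, the intervention-by-time term has (2 − 1)(k − 1) degrees of freedom:
- child activity: 5 − 1 = 4;
- self-efficacy and enjoyment: 4 − 1 = 3;
- family support: 3 − 1 = 2.

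The four outcomes in item ④ therefore need three different time factors. For two of them the time effect stops at the end of the intervention. Section 5.4.2 does not mention this.

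**The T3 term.** T0 and T4 name physiopathological indicators, followed by the activity questionnaire. T3 has *physical activity indicators* in the same position, again followed by a separate activity questionnaire. Read literally, body measures are not named at T3 (2 visits). Read as a slip for the T0 and T4 term, they are (3 visits). The second reading is more likely, because the literal one would list activity twice.

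**Timing.** Section 5.2 fills the experimental group first, and 5.3(1) says all its data are collected before controls are recruited. If the scales are added after some experimental T4 visits have passed, only part of that group has T4 scores. If they are added after the last one, only controls have them, and no between-group comparison is possible.

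**The case against.** Three stronger readings are tempting, and the documents do not support them.

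- A reader might infer that maintenance and end-of-intervention effects are lost for the trial as a whole. They are not. The primary outcome, parent activity and family support are collected at both T3 and T4, the two scales are collected at T3, and body measures at T4.
- A reader might infer that 5.2 and section 7 contradict each other. Section 5.2 lists visits and does not say that every instrument is used at each. Section 7 also leaves family support and body measures out of T1 and T2. The two sections are unreconciled, not in strict conflict.
- A reader might count the body measures as missing at T3. That rests on a term that is most likely a translation slip, so it is a wording query.

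The best case for leaving T4 alone is that no objective or hypothesis asks in terms whether self-efficacy or enjoyment persists, and no mediation analysis is planned. T4 also keeps family support and parent activity, which cover the parental side of the model. The background sentence "the long-term health effects of the intervention are unknown, requiring more data to support them" speaks of health effects, which activity and body measures address. All of this is fair, and it keeps the point to secondary outcomes. It does not explain why two outcomes that are measured at every earlier visit and named in hypothesis 2 drop out at the one follow-up visit, or why item ④ does not mention it. Ending their analysis at T3 would be a defensible choice if the plan stated it, but it does not.

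**Conclusion.** The point holds in a limited form. As section 7 stands, two declared secondary outcomes have no T4 data in either group, so their maintenance 3 months after the intervention cannot be estimated and cannot be recovered later. Effects on both scales up to the end of the intervention remain estimable. The primary outcome, its follow-up and the sample size are not touched.

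This assumes that the section 7 lists are complete and that staff follow them as written. The documents do not show whether experimental-group T4 visits have begun, which decides whether the full fix is still open. The T3 term and the visit sets in 5.4.2 are clarifications and add no established data loss.

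**What to change.** 1. Add the self-efficacy and enjoyment scales to the T4 list in section 7, before the first experimental-group T4 visit. If this cannot be done in time for both groups, state in section 7 and in 5.4.2 that the analysis of these two outcomes ends at T3.
2. Correct the T3 term so that it is clear that the same physiopathological indicators as at T0 and T4 are taken at the end of the intervention, if that is what is meant.
3. Put an instrument-by-visit table in section 7, refer to it from 5.2, and list in 5.4.2 the visits used for each outcome. Family support, for example, enters at T0, T3 and T4 only.

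The cost is two questionnaires at a visit that already takes place, so a few more minutes for families at T4. The other two changes are text only, unless body measures were truly not planned at T3. In that case taking them would add one measurement session.
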